### 7.2. Stopping Criteria

#### 7.2.1. Study Stopping Criteria

If one or more of the following criteria are met, the study will be temporarily paused, and all available safety data will be reviewed by the Sponsor and Investigator:

- A SAE occurring in 1 or more participants receiving GSK3923868 that is considered at least possibly related to the study drug;
- Two or more severe AEs occurring in a group of participants receiving GSK3923868 that are considered at least possibly related to the study drug.

Further participants may be dosed only if, after review, the Sponsor and Investigator considers it safe to do so.

#### 7.2.2. Pharmacokinetic Stopping Criteria

This protocol allows some alteration from the currently outlined dosing schedule, please refer to Section [6.5](#).

#### 7.2.3. Liver Chemistry Stopping Criteria

[figure not shown]
**Liver chemistry stopping, and increased monitoring criteria** have been designed to assure participant safety and evaluate liver event aetiology.

Discontinuation of study intervention for abnormal liver tests is required when:

- A participant meets one of the conditions outlined in [Figure 2](#).

OR

- In the presence of abnormal liver chemistry not meeting protocol-specified stopping rules, if the investigator believes that it is in the best interest of the participant.

**Figure 2 Phase 1 Liver Chemistry Stopping Criteria – Liver Stopping Event Algorithm**

Abbreviations: ALT = alanine transaminase; AST = aspartate transaminase; INR = international normalized ratio; SAE = serious adverse event; ULN = upper limit of normal.

#### 7.2.4. QTc Stopping Criteria

The Fridericia QT correction (QTcF) formula will be used in the study.

A participant that meets either bulleted criteria based on the average of triplicate ECG readings will be considered for withdrawal from the study intervention:

- QTcF > 500 msec
- Change from baseline: QTcF > 60 msec

Baseline QTcF will be based on the average of 3 predose ECGs collected on Day 1 (in Part A, Day 1 predose for each treatment period should be considered as baseline).

**Note:** Single safety ECG assessments are performed following enrolment in this study. If a single ECG should meet the criteria above, obtain two further ECGs over a brief period (e.g. 5 to 10 minutes). The averaged QTcF value of the 3 ECGs should be used to determine whether the participant should be withdrawn from the study.

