### 2.3.1. Risk Assessment

Potential Risk of Clinical Significance	Summary of Data/Rationale for Risk	Mitigation Strategy
Study Intervention [GSK3923868]		
Bronchospasm	Can potentially occur with any inhaled treatment.	
Inclusion/Exclusion criteria: In Parts A and B healthy participants with an FEV1 and an FVC < 80% of predicted normal value will be excluded. In Part C only participants with mild to moderate asthmatics with a pre-bronchodilator FEV1 > 65% of predicted normal value will be recruited.
 
Monitoring: All doses of study treatment will be administered in the clinical pharmacology unit in the presence of clinical staff. Spirometry will be conducted pre and post dose to monitor participants.
 
Management: Treatment with a short-acting inhaled bronchodilator will be available. If bronchospasm occurs GSK3923868 will be discontinued immediately. The participant will be assessed and, if necessary, further therapy will be given as deemed appropriate by the Investigator or the attending physician.
 
Participants will be withdrawn from the study if bronchospasm occurs.

Respiratory tract irritancy	In rats dosed for 4 weeks by inhaled administration, microscopic findings were noted in the lungs and bronchi, with minimal degeneration/regeneration of the epithelium at	Appropriate safety margin: Maximum clinical exposure at 3 mg are expected to be below the

Potential Risk of Clinical Significance	Summary of Data/Rationale for Risk	Mitigation Strategy

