### 6.5.2. Dose Escalation Stopping Criteria

Further dosing at the current dose level stops and that dose and no higher dose may be used if any of the following occur:

- Any one participant experiences a serious adverse event that is considered at least possibly related to the study drug.
- Two participants experience a severe adverse event or bronchospasm that is considered at least possibly related to the study drug.
- Three participants meet liver chemistry stopping criteria outlined in Section [7.2.3](#).
- Three participants meet QTc stopping criteria outlined in Section [7.2.4](#).
- Three participants meet spirometry stopping criteria outlined in Section [7.2.5](#).
- Three participants experience any adverse event considered clinically important by the Investigator.

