### 7.2.5. Spirometry Stopping Criteria

Any participant experiencing a reduction in FEV1 at the 1-hour post-dose time point compared to daily predose value of > 25% in Parts A and B and > 20% in Part C will be withdrawn from the study.

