### 7.2.6. Asthma Exacerbation Stopping Criteria (Part C Only)

Any participant experiencing an exacerbation of asthma must be withdrawn from the study. An asthma exacerbation is defined as follows:

- Episodes characterised by a progressive increase in symptoms of shortness of breath, cough, wheezing or chest tightness and progressive decrease in lung function, i.e. they represent a change from the patient's usual status that is sufficient to require a change in treatment [[GINA](#), 2020].
- A progressive decrease in lung function is defined as sustained drop in PEF of > 20 % from baseline (Day 1, predose) maintained for  $\geq 3$  days. In the absence of PEF measurements, Investigator judgement will be applied.

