### 7.2.8. Rechallenge

Study intervention restart or rechallenge after stopping criteria are met by any participant in this study is not allowed.

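### Section 7.2.4 leaves withdrawal discretionary after a confirmed QTcF above 500 msec; this conflicts with 7.2.8, which does not clearly reach daily dosing in Parts B and C

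*Protocol*

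**What the plan says.** Protocol 7.2.4 sets two QTc thresholds, both judged on the mean of triplicate ECGs: QTcF above 500 msec, and a rise of more than 60 msec from baseline. A participant who meets either "will be considered for withdrawal from the study intervention". The Note covers a single post-enrolment ECG that crosses a threshold. Two more are taken, and then: "The averaged QTcF value of the 3 ECGs should be used to determine whether the participant should be withdrawn from the study".

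The other rules for individual participants are worded differently:

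- Liver (7.2.3): "Discontinuation of study intervention for abnormal liver tests is required when" the listed conditions are met.
- Spirometry (7.2.5): anyone with an FEV1 fall of more than 25% "in Parts A and B and > 20% in Part C will be withdrawn from the study".
- Exacerbation (7.2.6): "Any participant experiencing an exacerbation of asthma must be withdrawn from the study".
- Bronchospasm (2.3.1): "Participants will be withdrawn from the study if bronchospasm occurs".

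Two further sections bear on the point. Section 7.2.8 states: "Study intervention restart or rechallenge after stopping criteria are met by any participant in this study is not allowed". Section 6.5.2 closes a dose level, and all higher ones, when "Three participants meet QTc stopping criteria".

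**The concern.** The section is titled as a stopping criterion and already has a confirmation step, yet the action that follows confirmation is only to consider withdrawal. The liver rule shows the contrast. There, investigator judgement is kept for values that fall short of the stopping thresholds; here, judgement applies after the threshold has been crossed.

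The discretion also sits badly with 7.2.8. One section allows a participant who meets the criterion to stay on study intervention. Another forbids restart or rechallenge once a stopping criterion has been met. A site has to work out for itself how the two fit together.

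At stake is the safety of one participant in a first-in-human study. Removal at the higher QTc threshold should not depend on which of two sections a site gives more weight.

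**Working it through.** **1. What happens to one participant with a confirmed QTcF above 500 msec**

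| Setting | 7.2.4 | 7.2.8, plain reading (criterion met) | 7.2.8, narrow reading (treatment was stopped) |
|---|---|---|---|
| Part A, single doses at least 10 days apart | Consider withdrawal | A later dose is barred | Not engaged unless the participant was withdrawn |
| Parts B and C, daily dosing | Consider withdrawal | Unclear: with no interruption there is no obvious restart or rechallenge | Not engaged |

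The plain reading is the better one for Part A. The trigger in 7.2.8 is that criteria are met, 7.2.4 is titled as stopping criteria, and 6.5.2 calls them that. A new dose after a washout is naturally a rechallenge. In Parts B and C the next daily dose simply continues treatment, so the discretion in 7.2.4 matters more there.

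**2. Doses affected in Parts B and C**

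Inputs: planned 3000 mcg daily for 14 days (Part B) and 7 days (Part C), from Protocol 6.1; a safety ECG 6 hours after dosing on Day 1, from the Schedule of Activities; 12 planned active participants in each part, from 9.2.

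If the criterion is first met at the Day 1 post-dose ECG, the remaining planned doses are 14 − 1 = 13 in Part B and 7 − 1 = 6 in Part C. These are maxima; a later event leaves fewer.

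**3. Whether 6.5.2 fills the gap (illustrative)**

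It acts on dose levels, so it does not remove the individual even when triggered. To show how seldom it would be triggered, take the generic 5% and 20% adverse outcome rates in 9.2 and assume independent participants.

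The protocol's own figures first. P(0) = (1 − p)^n gives 63.0% and 13.4% for n = 9, and 54.0% and 6.9% for n = 12. These match the stated 63%, 13%, 54% and 7%. From the binomial distribution:

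| n active | p | P(at least 1) | P(at least 3) | Trigger not reached, given at least 1 |
|---|---|---|---|---|
| 9 (a Part A dose) | 5% | 37.0% | 0.8% | (0.370 − 0.008)/0.370 = 98% |
| 9 | 20% | 86.6% | 26.2% | (0.866 − 0.262)/0.866 = 70% |
| 12 (Part B or C) | 5% | 46.0% | 2.0% | (0.460 − 0.020)/0.460 = 96% |
| 12 | 20% | 93.1% | 44.2% | (0.931 − 0.442)/0.931 = 53% |

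**4. Part A context: where the narrow reading would matter**

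Table 2 of the protocol has four sequences of three participants per cohort, with planned doses 50/100/250 and 500/1000/3000 mcg. Active participant-periods: 9 × 3 × 2 = 54. Those followed by a later active dose:

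- Cohort 1: 6 at 2 times, 6 at 2.5 times, and 3 at 5 times the dose after an intervening placebo period.
- Cohort 2: 6 at 2 times, 6 at 3 times, and 3 at 6 times the dose after placebo.

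The total is 15 + 15 = 30 of 54. This counts planned transitions. It is not a risk, and it is relevant only if 7.2.8 is read narrowly.

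**The case against.** The strongest reply is that 7.2.8 already settles Part A. That stands. A reader might infer from 7.2.4 alone that someone with a confirmed QTcF above 500 msec can go on to a higher dose in the next period. The documents do not support this as a plain statement, because 7.2.8 applies once criteria are met and, on its natural reading, forbids that dose. What is left in Part A is a conflict between two sections, with a narrower reading available to a site.

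A second reply is that the Note makes the averaged value decisive. It makes that value the basis for the decision, but it does not say what the decision must be, and it does not override the action sentence.

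A third is that other safeguards exist: sponsor discussion of immediate safety concerns (Section 8), investigator discretion to withdraw (7.3), the study pause for one related SAE or two related severe AEs (7.2.1), the single related SAE rule in 6.5.2, and Dose Escalation Committee review before each Part A dose level and before Parts B and C (9.5.1). They make continued dosing unlikely. None requires that the individual be removed for QTcF above 500 msec. The listed SAE criteria (10.3.2) do not name this threshold, so an asymptomatic case would rest on judgement.

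A fourth is that the evidence is incomplete. This also stands: parts of the ECG sections are redacted and the Dose Escalation Plan is not supplied. The most that can be said is that no visible section contains a compulsory rule.

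Finally, the percentages and the 30 of 54 count could be mistaken for the size of the problem. They are not. The rates are generic, entry is barred at screening QTcF above 450 msec, and the visible study-drug risks in 2.3.1 are respiratory.

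**Conclusion.** The point holds as an inconsistency with a safety consequence. Section 7.2.4 makes removal discretionary after a confirmed QTcF above 500 msec, the comparable rules make it compulsory, and 7.2.8 points the other way. The clearer gap is daily dosing in Parts B and C, where 7.2.4 as written permits up to 13 or 6 further planned doses of 3000 mcg. In Part A the problem is ambiguity, not an open route to a higher dose.

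The frequency cannot be estimated because the documents give no QTc event rate. A confirmed value above 500 msec is likely to be much rarer than 5%, and then the three-participant trigger would be reached less often still. The dose counts assume the planned dose and duration, and the probabilities assume independent participants. No sample size or analysis result changes. The change should be made because it is cheap and closes a gap in a stopping rule; nothing here suggests the study is unsafe as a whole.

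**What to change.** Amend 7.2.4 in two places.

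1. Action sentence: *If the mean of the triplicate ECGs gives QTcF > 500 msec, the participant will be withdrawn from study intervention and will receive no further doses in any part or period.*
2. Note: say that the averaged QTcF is used *to apply these criteria*.

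Whether a rise of more than 60 msec should also compel withdrawal is for the sponsor to decide. If that limb stays discretionary, the protocol should say whether 7.2.8 applies to it; otherwise the same conflict remains there. Section 6.5.2 can stay as it is.

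The cost is a short amendment, or a little more if the 60 msec limb needs clarifying, with no added visits or procedures. The downside is a rare extra withdrawal, which 7.3 allows to be replaced at the Medical Monitor's discretion in consultation with the Principal Investigator.

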### 7.2.5. Spirometry Stopping Criteria

Any participant experiencing a reduction in FEV1 at the 1-hour post-dose time point compared to daily predose value of > 25% in Parts A and B and > 20% in Part C will be withdrawn from the study.

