**Footnotes to Part B: Repeat Dose Repeat Dose | Healthy Participants (Cohorts 3 and 4)**

1. Day -1 inhaler training may be performed on Day 1 if needed and before administration of the first dose. Additional training may be provided as needed and according to Investigator discretion.
2. To be performed according to local site procedures. Day 4 to 6 test is required for Cohort 4 only ahead of bronchoscopy on Day 7. Day 12 to 14 test is required for Cohort 3 only ahead of bronchoscopy on Day 15. Additional ad hoc testing may be implemented based on local site procedures.
3. Predose and 1-hour post-dose only.
4. Includes systolic and diastolic blood pressure, heart rate, respiration rate and tympanic temperature.
5. Predose.
6. On treatment days ECGs will be collected at predose and 6-hours post-dose. On Day 1 predose, triplicate measurements will be collected, and the mean values will be used to calculate baseline. At all other times single ECGs can be taken.
7. Cardiac telemetry to start approximately 1-hour pre-dose and continuously until 6 hours post dose.

CCI

9. Clinical Chemistry and Haematology at all visits. Coagulation will be assessed on Day 4 for both cohorts.
10. At pre-dose, 5 min, 30 min, 45 min, 1 h, 2 h, 4 h, 6 h, 8 h, 12 h and 16 h.

CCI

16. At 15 min.

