**Footnotes to Part C: Repeat Dose | Asthma (Cohort 5)**

1. Day -1 inhaler training may be performed on Day 1 if needed and before administration of the first dose. Additional training may be provided as needed and according to Investigator discretion.
2. To be performed according to local site procedures. Additional ad hoc testing may be implemented based on local site procedures.
3. Predose and 30 min only.
4. PEF measurements will be taken in triplicate twice each day (once in morning upon waking and once in the evening before bedtime) from Day -1 evening until discharge on Day 8. Clinical site staff will complete and record the PEF measurements at each time point.
5. Provide PEF device refresher training if necessary.
6. Includes systolic and diastolic blood pressure, heart rate, respiration rate and tympanic temperature.
7. Predose only
8. On treatment days ECGs will be collected at predose and 6-hours post-dose. On Day 1 predose, triplicate measurements will be collected, and the mean values will be used to calculate baseline. At all other times single ECGs can be taken.
9. Cardiac telemetry to start approximately 1-hour pre-dose and continuously until 6 hours post dose.
10. Clinical Chemistry and Haematology only.
11. At pre-dose, 5 min, 15 min, 30 min, 45 min, 1 h, 2 h, 4 h, 6 h, 8 h, 12 h and 16 h

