4.2.1. Definition of endpoints

Adverse events will be coded using the standard Medical Dictionary for Regulatory Affairs (MedDRA dictionary).

Grade 1 AEs are defined as mild. Grade 2 or higher AEs are defined as moderate or severe. This study will report AEs as mild, moderate or severe.

A study intervention-related AE/SAE is defined as an AE/SAE for which the investigator classifies the possible relationship to study intervention as "Yes". A worst-case scenario approach will be taken to handle missing relatedness data, i.e. the summary table will include events with the relationship to study intervention as 'Yes' or missing.

Spirometry assessments are performed in triplicate with the highest value reported.

Clinically significant values are defined as:

- Values in the potential clinical interest (PCI) ranges for laboratory values, vital signs and ECGs
- Values that achieve the study stopping criteria (protocol section 7.2.5) for spirometry

The same PCI ranges will be used for both healthy volunteers and stable asthmatics, with all ranges being defined in the OPS.

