4.2.2.2. Laboratory Data, Vital Signs, ECGs and Spirometry

For laboratory data, separate tables for haematology, clinical chemistry and urinalysis tests will be produced. Liver biochemical parameters will be included with clinical chemistry tests. Vital signs data will include semi supine systolic and diastolic blood pressure, pulse rate, respiratory rate and temperature measurements.

ECG data will include PR, QRS, QT and QTcF intervals.

Spirometry data will include FEV₁ and FVC measurements.

For haematology, clinical chemistry, urinalysis, vital signs, ECG and spirometry data the following information will be summarised:

1. Clinically significant values at each visit
2. Raw and change from baseline values at each visit

Note: The first table is the only one included as part of the primary endpoint. [redacted]

[redacted]

In order to detect potential bronchospasms, an additional table for spirometry values will be produced which summarises the changes between daily pre- and post-dose FEV₁ and FVC values.

For ECGs, a figure plotting the baseline QTcF and the worst-case post-baseline values will be produced. The figure will have reference lines at 480 and 500 msec for both the ordinate and the abscissa axes. There will be diagonal reference lines at equality (i.e. a 45 degree line), at equality plus 30 msec, and at equality plus 60 msec.

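### The Part C FEV1 stopping rule is tied to a 1-hour reading that the Part C schedule does not collect, so neither the rule nor the primary spirometry event can be met at a scheduled assessment

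*Protocol*

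**What the plan says.** **The rule.** Protocol 7.2.5 withdraws any participant with a "reduction in FEV1 at the 1-hour post-dose time point compared to daily predose value" beyond a threshold: more than 25% in Parts A and B, more than 20% in Part C. One time point is given for all Parts.

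**The schedule.** In the Part C Schedule of Activities, spirometry on Days 1 to 7 carries footnote 3: "Predose and 30 min only". Day 8 has one reading, 24 hours after the Day 7 dose, with no dose that day. The corresponding Part B footnote, for Day 1, reads "Predose and 1-hour post-dose only", which fits the rule.

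**What depends on the rule.**
- Protocol 6.5.2 halts dosing at a level if "Three participants meet spirometry stopping criteria outlined in Section" 7.2.5.
- SAP 4.2.1 defines clinically significant spirometry as "Values that achieve the study stopping criteria (protocol section 7.2.5) for spirometry".
- SAP 4.2.2.2 lists a table of clinically significant values and a table of raw and change-from-baseline values, and notes: "The first table is the only one included as part of the primary endpoint". The first table is the one of clinically significant values.

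**The concern.** The rule needs a value that the schedule does not produce. Part C is the first exposure of people with asthma to the drug, at a planned 3000 mcg daily for 7 days, and bronchospasm is the first drug risk listed in protocol 2.3.1. The protocol sets a tighter limit for these participants than for healthy ones, yet this is the Part where the limit has no scheduled reading behind it.

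Two things are at stake.

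- **Safety.** This is the only numeric rule for an acute FEV1 fall after dosing in Part C. The other numeric lung-function rule, for exacerbation in 7.2.6, needs a "sustained drop in PEF of > 20 % from baseline (Day 1, predose) maintained for" at least 3 days. PEF is taken on waking and at bedtime, not relative to the dose, so that rule cannot act on an acute post-dose fall.
- **Reporting.** The primary spirometry table for Part C, programmed as the SAP defines it, would show no events from scheduled data whatever the 30-minute readings were. A reader could take that as evidence of good tolerability.

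**Working it through.** **1. Time points side by side**

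| Item | Time after dose |
|---|---|
| Rule, protocol 7.2.5, all Parts | 1 h |
| Part B, Day 1 (SoA footnote 3) | 1 h |
| Part C, Days 1–7 (SoA footnote 3) | 0.5 h |
| Part C, Day 8 | 24 h after the Day 7 dose |

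The Part C times and the rule do not overlap, and the word *only* in the footnote excludes a further routine reading.

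**2. Number of sessions affected**

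Part C has 16 participants (12 active, 4 placebo) and 7 dosing days.

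- Scheduled post-dose sessions on dosing days: 16 × 7 = 112
- Active: 12 × 7 = 84; placebo: 4 × 7 = 28
- Scheduled at 1 hour: 0

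**3. The plan's own figures**

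Protocol 9.2 and SAP section 5 give the chance of seeing no event in 12 active participants as 54% at a true rate of 5% and 7% at 20%. With P(0) = (1 − p)^12:

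- p = 0.05: 0.95^12 = 0.540
- p = 0.20: 0.80^12 = 0.069

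Both reproduce.

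**4. What a rule matched to the schedule could detect**

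The documents give no rate for FEV1 falls. Assume that p is the chance that a participant has a fall of more than 20% at the measured time point at least once, that participants are independent, and that only the 12 active participants are counted. Then

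- P(at least 1) = 1 − (1 − p)^12
- P(at least 3) = 1 − [(1 − p)^12 + 12p(1 − p)^11 + 66p²(1 − p)^10]

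For p = 0.20: P(at least 1) = 1 − 0.069 = 0.931, and P(at least 3) = 0.442. For p = 0.05: P(at least 1) = 1 − 0.540 = 0.460, and P(at least 3) = 0.020. Two further rates show the range.

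| Assumed rate | At least 1 of 12, 30-minute rule | At least 3 of 12, 30-minute rule | Either, 1-hour wording at scheduled assessments |
|---|---|---|---|
| 5% | 46% | 2% | 0% |
| 10% | 72% | 11% | 0% |
| 20% | 93% | 44% | 0% |
| 30% | 99% | 75% | 0% |

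The last column follows from step 1 and does not depend on the assumed rate.

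**The case against.** The wording conflict is not in dispute. The case on the other side is that little follows from it.

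**The primary table need not be empty.** Protocol 9.4.1.2 takes clinically significant measurements from any time between randomisation and follow-up into the primary endpoint, FEV1 included. A programmer might therefore apply the 20% threshold to the 30-minute value. But that section says when a significant value counts, not what makes it significant. For spirometry the only definition is SAP 4.2.1, which points to 7.2.5 and its 1-hour reading. Using the 30-minute value would be sensible, but it would depart from the written definition.

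**Falls are still seen and acted on.** This largely stands.
- FEV1 is measured at 30 minutes on all seven dosing days.
- Protocol 2.3.1 states: "Participants will be withdrawn from the study if bronchospasm occurs".
- Under 6.5.2, two related bronchospasm cases stop dosing at that level, fewer than the three participants the spirometry trigger needs.
- The investigator may withdraw anyone for safety. An abnormal finding judged clinically significant can be reported as an adverse event, subject to the underlying-disease exception, and adverse events are themselves a primary endpoint.
- The SAP adds a table of daily pre- to post-dose FEV1 and FVC changes.
- No higher dose follows Part C, so the 6.5.2 trigger could only halt the remaining Part C dosing.

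These protections narrow the loss but do not remove it. The withdrawal routes rest on clinical judgement, bronchospasm has no numeric definition, and the extra table is outside the primary endpoint and withdraws no one.

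**Other documents or flexibility may resolve it.** Spirometry procedures are in the Study Reference Manual, data handling conventions are in the Output and Programming Specification, and assessment times may change on emerging data. Neither document is available here. Permission to change a time does not schedule a reading. An unscheduled 1-hour reading is possible, but rescue SABA is allowed at any time, so a fall at 30 minutes could be treated before the hour.

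**The event rates are generic.** This stands: 5% and 20% are the plan's illustrations for any adverse outcome. The zero at scheduled assessments does not rest on them.

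**Conclusion.** The concern holds. No scheduled Part C reading can satisfy 7.2.5: 0 of 112 post-dose sessions on dosing days are at 1 hour, and Day 8 follows no dose that day. The individual withdrawal rule, the spirometry trigger in 6.5.2 and the spirometry component of the Part C primary endpoint are therefore without effect at scheduled assessments.

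The claim is limited to scheduled assessments and to the rule as written. An unscheduled 1-hour reading, or a documented timing change, could bring the rule into play, but neither is planned. Primary safety evaluation through adverse events is unaffected. An empty Part C spirometry table produced under the written definition would reflect the mismatch in times and should not be read as observed tolerability. The detection probabilities are illustrative, because the rate of FEV1 falls is an assumption.

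**What to change.** In protocol 7.2.5, give the criterion by Part. For Part C, use a fall of more than 20% in FEV1 from the same-day predose value at the scheduled 30-minute reading; leave Parts A and B at 1 hour. In SAP 4.2.1, define clinically significant spirometry with the same Part-specific time point. The trigger in 6.5.2 then works without change, because it refers to 7.2.5.

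The alternative is to change Part C SoA footnote 3 from 30 minutes to 1 hour, which would align the schedule with the existing rule.

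The cost is one line in the protocol and one line in the SAP. No extra participants are needed, and the 30-minute option adds no assessments.
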